Samples obtained 14 days following receipt of vaccine #3 (study day 182) and #4 (study day 554) in the highest antigen dose arms (Pfs25M, 47µg alone; Pfs230D1M, 40µg alone; Pfs25M, 47µg + Pfs230D1M, 40µg; TWINRIX [received TWINRIX for first 3 doses, then Menactra® for fourth dose]). Vaccinations received at 0, 1, 6 months (2015) and 18 months (2016). Each individual data points represents an individual ELISA or SMFA results. Black bars represent 95% confidence intervals. Red asterisk represent statistical significance when compared to the control (TWINRIX). Tables report the mean TRA (95% confidence intervals) following the third and fourth vaccination.

In 2015, starting 1 week post vaccination #3 and using 60 mosquitoes total, 2005 DSF were performed in 175 individuals, of which 73% participated in all 12 feeds. Fifty-eight (2.9%) of the DSFs resulted in a positive DSF in 18 (10.3%) unique individuals. In 2016, starting 1 week post vaccination #4 and using 30 mosquitoes total, 1843 DSFs were performed in 160 individuals, of which 87% participated in all 12 feeds. Thirty (1.6%) of the DSFs resulted in a positive DSF in 18 (11.3%) unique individuals. Analysis of the DSFs (accounting for all positive DSFs) post vaccination #4 using two models (GEE, GLMM) showed no significant difference in DSF results between Pfs230 alone, Pfs25M + Pfs230 in combination, and the control group. Pfs25M alone, when compared to the control group, in the GEE analyses did show a significant odds ratio of

infection (OR 6.75; 95% CI 1.16-39.35; $p=0.034$) but this significance was not seen in the GLMM analyses (OR 3.05; 95% CI 0.14-65.89; $p=0.633$). Further analyses are ongoing to account for possible transmission by other *Plasmodium* species (*P. ovale*, *P. malariae*), vaccine variants, and the impact of time post vaccination on DSF transmission events.

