Using blinded SMFA data from #15-I-0044, a WMWT comparing 60 TRAs of the vaccine arm to 60 TRAs of the control, we anticipate at least 80% power to detect a difference in TRAs of 18% (simulation-based power calculations). If TBAs are used, we will standardize the TBAs to a common target control mean first. The standardization will utilize the estimand that comes from a zero-inflated negative binomial with random effects for feed and container of mosquito. TRAs can be combined across feeds or calculated within feeds as they do not require the same standardization as that of TBAs.

DSF

Using the data from the primary DSF evaluation period of study #13-I-N109 and #15-I-0044 we were able to do power calculations for this study. The power calculations are quite sensitive to the infectivity rate, which varies from year to year. Taking a weighted average of 2014 and 2015 data we estimate infectivity was 14.8% (the percentage of subjects in the control arm that had at least one positive DSF). Using this same % and comparing 108 subjects (this number assumes 10% dropout) of the combined Arms 2c and 2d we will have ~85% power to detect 80% vaccine effect through the (0,1) infective/non-infective way of quantifying each DSF with 32 DSF per person and 30 mosquitoes per cup. The (0,1) infective/non-infective way of quantifying each DSF involves declaring a cup as infective if any of the 30 mosquitoes is infected and conversely non-infective if and only if all 30 mosquitoes are not infected. While combining arms that have full dosing in one and fractional dosing in the other assumes they are having similar effects, this assumption is deemed acceptable in order to power the analysis. If infectivity drops to 10.3%, then the power to detect 80% vaccine effect under same conditions is about 40%. It is important to note that in 2016 only 15 mosquitoes were used per cup and only 12 DSFs per person were conducted. Thus, we are treating the 10.3% infectivity as a “worse case scenario” for the 30 cup / 24 DSFs set-up as proposed in this protocol. A binomial family GEE model will be used to account for repeated measurements.

On average each feed week we had about 3% positivity over all subjects. The (0,1) infective/non-infective way of quantifying DSF is likely an over-simplification of the true system. As well, this way of quantifying the DSF will have lower power when the vaccine is leaky rather than all or nothing.

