For the booster (dose 4), the combined Arms 2c and 2d will be evaluated vs. controls as the primary endpoint.

DSF in conjunction with SMFA

As there will be simultaneous blood draws, a unique opportunity to investigate SMFA predicting zero inflated DSF measurements will be pursued. Simple linear regression models will be explored.

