14.6 Randomization

See [Section 8.2](#) for more information.

Enrollment into the Bamako/Sotuba, Mali portion of the study will be randomized as follows:

- Arms 1a and 2a will be enrolled 1-1 with random block based on time of enrollment/randomization;
- Arm 3a will not have a concurrent arm, so there will be no randomization for that arm;
- Arms 1b, 2b and 4a will be enrolled 1-1-1 with the same style of random block based on time of enrollment/ randomization;
- Arms 3b and 4b will be enrolled 1-1 with random block based on time of enrollment/randomization.

Enrollment into the Bancoumana/Doneguebougou, Mali portion of the study will be randomized in random blocks of size no greater than 8 and stratified by village. In order to accomplish this, a list of all enrolled subjects will be given to the study statistician for the first randomization. As subjects that dropout after randomization, and are not vaccinated, cannot be replaced, randomization and first vaccination should occur as close in time as possible to avoid having subjects in the ITT efficacy and safety analyses that have never received vaccination or comparator. Randomization lists are not produced pre-enrollment to reduce the risk of on-site operational error in randomization assignment, which given the stratified nature of the randomization would require management of several lists.

Randomization will occur **between arms** as follows in the Bancoumana/Doneguebougou study:

- Arms 2c, 2d, and 4c will be enrolled 1-1-2 with random block sizes no greater than 8.

Randomization between the arms allows for causal comparisons of ELISA and functional assay responses.

15 Human Subject Protections and Ethical Obligations

This research will be conducted in compliance with the protocol, Good Clinical Practices (GCP), and all applicable regulatory requirements.

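### The binomial GEE for the sparse direct skin feed (DSF) outcome has no rule for a vaccine group with no positive feed, and the stated powers of about 85% and 40% do not fit one test

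*Combined protocol and SAP*

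**What the plan says.** Section 14.5 (DSF) scores each feed as infective or not. From earlier seasons it takes control infectivity: "we estimate infectivity was 14.8% (the percentage of subjects in the control arm that had at least one positive DSF"). The power statement is based on "comparing 108 subjects (this number assumes 10% dropout) of the combined Arms 2c and 2d" and claims about "85% power to detect 80% vaccine effect through the (0,1) infective/non-infective way of quantifying each DSF with 32 DSF per person". For a poorer season it adds: "If infectivity drops to 10.3%, then the power to detect 80% vaccine effect under same conditions is about 40"%. The analysis is then given in one sentence: "A binomial family GEE model will be used to account for repeated measurements". The same section remarks that this scoring loses power when the vaccine is leaky rather than all-or-nothing. For dose 4 it states: "For the booster (dose 4), the combined Arms 2c and 2d will be evaluated vs. controls as the primary endpoint".

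The section does not give the link, working correlation, variance estimator, small-sample correction, test (Wald or score), village term, significance level, or a rule for a group with no positive feed. It does not say which test or simulation produced 85% or 40%. It bases the 85% on 32 feeds per person, but describes the design as having 24 when it discusses 10.3%.

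**The concern.** Few vaccinees are expected ever to infect a mosquito. At the planned effect the expected number is about 3 of 108, and about 2 in a poorer season. A logistic model has no finite odds ratio if that number is zero, and zero becomes more likely as the vaccine improves. The plan would then have no defined estimate or p-value in the case it most hopes for.

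The power statement is the second issue. Readers will take 85% and 40% as properties of the GEE. If no single analysis yields both, the sponsor cannot tell how likely the trial is to detect the effect it was sized for, or how far a low-transmission season would hurt it.

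**Working it through.** **Inputs.** Control infectivity is 14.8% or 10.3%, the effect is 80%, and 108 vaccinees are analysed, since 120 × 0.9 = 108 (Section 14.5). Allocation is stated as "Arms 2c, 2d, and 4c will be enrolled 1-1-2 with random block sizes no greater than 8" (Section 14.6), so Arm 4c also has 120 subjects. The same 10% dropout is assumed there, giving 108. A two-sided 0.05 level is assumed, as in the ELISA paragraph of Section 14.5. Missed feeds are ignored.

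**Reproducing the stated power.** The subject-level rates are 14.8% v 0.2 × 14.8% = 2.96%, and 10.3% v 2.06%. Enumerating both binomials with 108 per group, Fisher's exact test on ever-infective status has power 85.1% and 65.5%. The first matches the plan. The second does not match about 40%.

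**Vaccine group with no positive feed (all-or-nothing action).** P(none) = (1 − rate)^108.

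| Effect | 14.8% infectivity | 10.3% infectivity |
|---|---|---|
| 80% | (1 − 0.0296)^108 = 3.9% | (1 − 0.0206)^108 = 10.6% |
| 90% | (1 − 0.0148)^108 = 20% | (1 − 0.0103)^108 = 33% |
| 95% | (1 − 0.0074)^108 = 45% | (1 − 0.00515)^108 = 57% |

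A trial example had 16 of 108 controls infective and no vaccinee. Fitted in statsmodels, it gave coefficient −26.9, robust SE 0.32 and p = 0, flagged as converged, under both independence and exchangeable working correlations. The standard error is meaningless because the estimate is on its way to minus infinity.

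**The GEE, taken as a robust Wald test.** This is an assumption. With 32 feeds each, let y be a subject's positive feeds and p the group's share of positive feeds. The log-odds ratio is logit(p₁) − logit(p₀). Its robust variance is the sum over the two groups of Σ(y − 32p)² / [32·n·p(1 − p)]².

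The number of positive feeds per infective subject is about 0.03 × 32 / 0.148 = 6.5, using the roughly 3% feed positivity in Section 14.5. Scaling the earlier seasons in Section 3.1.4.2 to 32 feeds gives about 4.6 (30 positives in 18 people) and 9.0 (58 in 18). The variance of these counts is not documented, so the coefficient of variation (CV) was set between 0.5 and 1.1. Leaky action was simulated as each would-be positive feed surviving with probability 0.2.

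| Power, mean 6.5 | GEE, CV 0.7 | GEE, CV 1.1 | Stated |
|---|---|---|---|
| 14.8%, all-or-nothing | 67% | 58% | ~85% |
| 14.8%, leaky | 94% | 84% | |
| 10.3%, all-or-nothing | 47% | 44% | ~40% |
| 10.3%, leaky | 83% | 72% | |

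Over all clustering settings tried, the ranges are 58-75% and 84-94% at 14.8%, and 44-49% and 67-83% at 10.3%. Trials with no positive vaccine feed were counted as not significant. Counting them all as significant adds 2.9 to 4.1 points to the all-or-nothing rows at 14.8% (70% and 62%) and 9.5 to 11.3 points at 10.3% (58% and 54%). Either way, no test tried gives both 85% and 40%.

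**Type I error of the same test.** With counts scaled to 32 feeds it was 5.2-5.5% at 14.8% and 5.5-6.2% at 10.3% for CV 0.5-0.7, and 6.8-7.3% and 7.2-8.9% for CV 0.9-1.1. With the counts seen over 12 feeds it was 4.6-5.3%.

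**The case against.** The strongest reply is that the plan names a model and not a test. A score test or a bias-corrected sandwich would fit the text, so the Wald figures describe one reading of it. That stands, and it is why those figures are labelled as an assumption. It does not help with a group that has no positive feed, because the odds ratio is infinite under any variance estimator.

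Four stronger readings are tempting, and the documents do not support them.

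- *The GEE is badly oversized.* The pooled test is near nominal under moderate clustering. The inflation to about 9% needs a clustering variance that the documents do not give.
- *The 85% is really a Fisher calculation.* Fisher matches 85% but misses 40% by about 25 points. GEE power under leaky action also spans 85%. The source is unstated, and no more can be said.
- *The earlier study proved the GEE unreliable.* Section 3.1.4.2 reports a significant GEE odds ratio, "but this significance was not seen in the GLMM analyses". The GEE interval 1.16-39.35 around 6.75 implies SE = 3.52/3.92 = 0.90, z = 1.91/0.90 = 2.12 and p = 0.034, as printed. The GLMM interval 0.14-65.89 around 3.05 implies SE = 6.15/3.92 = 1.57, z = 1.115/1.57 = 0.71 and p of about 0.48, not the printed 0.633. The two models also estimate different odds ratios. The disagreement shows that results on this outcome depend on the model; it does not show that the GEE is at fault.
- *A permutation test should replace the GEE p-value.* It holds its size (4.1-5.2% for total positive feeds) and is defined with no positive feed. Under leaky action its power was 86% and 71% against 94% and 84% at 14.8%, and 63% and 52% against 83% and 72% at 10.3%. Further runs put the loss at 6-17 and 8-28 points. Part of that gap is the Wald test's excess size, but it is a real trade-off.

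It is also fair that Section 14.1 calls the study exploratory and Section 5.2.2 lists DSF as secondary. Yet Section 14.5 makes the pooled comparison primary for dose 4, and Section 3.6 makes measurable activity the trigger for later combination trials.

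**Conclusion.** Two defects hold. First, the named analysis is undefined when the vaccine group has no positive feed. At the design effect this occurs in 3.9% of trials at 14.8% infectivity and 10.6% at 10.3%, rising to 20% and 33% at a 90% effect, and no rule covers it. These figures assume all-or-nothing action and 108 analysed vaccinees.

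Second, the stated powers cannot be tied to the named analysis or to each other. Section 14.5's remark on leaky vaccines suggests that the 85% assumes all-or-nothing action, where the assumed robust Wald GEE reaches 58-75%. The simulated ranges rest on 108 controls, two-sided 0.05, 32 complete feeds and an assumed clustering variance.

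A reader might infer that the GEE is invalid for this trial. The size results do not support that: about 5-7% with moderate clustering and at most about 9% in the pooled comparison. One further limit applies to dose 4. Subjects re-enrol after unblinding (Section 5.1.2), so the randomisation basis is weaker there for any test, including a permutation test.

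**What to change.** 1. Keep the GEE, and state its link, working correlation, variance estimator and test. Add: if either group has no positive feed, or the fit separates, the odds ratio and its p-value are replaced by the difference in the proportion of subjects ever infective, with exact confidence interval and exact p-value. With no true effect the trigger is very rare, since (1 − 0.103)^108 is about 0.00001 per group, so the rule barely affects type I error.
2. Recompute and restate power at 14.8% and 10.3% for that named procedure, fallback included, under both all-or-nothing and leaky action, with the clustering assumptions shown. Reconcile 32 with 24 feeds per person. Twice-weekly feeding for 12 weeks after dose 3 gives 24, and for 16 weeks after dose 4 gives 32, so each power figure should say which period it covers.
3. Add a permutation p-value as a sensitivity analysis, following the village strata and the randomisation blocks of Section 14.6. Fix its statistic in advance, including how subjects with few feeds are weighted. Note the weaker randomisation basis when it is applied to dose 4.

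The cost is a paragraph of analysis wording, one simulation and a short program. Sample size and data collection do not change. The restated power may be below 85%.

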14.6 Randomization

See [Section 8.2](#) for more information.

Enrollment into the Bamako/Sotuba, Mali portion of the study will be randomized as follows:

- Arms 1a and 2a will be enrolled 1-1 with random block based on time of enrollment/randomization;
- Arm 3a will not have a concurrent arm, so there will be no randomization for that arm;
- Arms 1b, 2b and 4a will be enrolled 1-1-1 with the same style of random block based on time of enrollment/ randomization;
- Arms 3b and 4b will be enrolled 1-1 with random block based on time of enrollment/randomization.

Enrollment into the Bancoumana/Doneguebougou, Mali portion of the study will be randomized in random blocks of size no greater than 8 and stratified by village. In order to accomplish this, a list of all enrolled subjects will be given to the study statistician for the first randomization. As subjects that dropout after randomization, and are not vaccinated, cannot be replaced, randomization and first vaccination should occur as close in time as possible to avoid having subjects in the ITT efficacy and safety analyses that have never received vaccination or comparator. Randomization lists are not produced pre-enrollment to reduce the risk of on-site operational error in randomization assignment, which given the stratified nature of the randomization would require management of several lists.

Randomization will occur **between arms** as follows in the Bancoumana/Doneguebougou study:

- Arms 2c, 2d, and 4c will be enrolled 1-1-2 with random block sizes no greater than 8.

Randomization between the arms allows for causal comparisons of ELISA and functional assay responses.

15 Human Subject Protections and Ethical Obligations

This research will be conducted in compliance with the protocol, Good Clinical Practices (GCP), and all applicable regulatory requirements.

15.1 Institutional Review Board

A copy of the protocol, informed consent forms, and other study related information to be completed by subjects, such as questionnaires, diary cards, medical history forms, and any proposed advertising/recruitment materials or letters to the subjects will be submitted to the reviewing IRBs for written approval. The investigator must submit and obtain approval from the IRBs for all subsequent amendments to the protocol, informed consent documents, and other study documentation referenced above. The investigator will be responsible for obtaining IRB approval of the annual Continuing Review throughout the duration of the study. The investigators will notify the reviewing IRBs of protocol violations and SAEs as specified in the relevant sections of the protocol.

15.2 Informed Consent Process

Informed consent is a process where information is presented to enable persons to voluntarily decide whether or not to participate as a research subject. It is an on-going conversation between the human research subject and the researchers which begins before consent is given and continues until the end of the subject's involvement in the research. Discussions about the research will provide essential information about the study and include: purpose, duration, experimental procedures, alternatives, risks and benefits. Subjects will be given the opportunity to ask questions and have them answered.

Consent forms will be approved by all participating IRBs. The subjects will sign the informed consent document prior to undergoing any research procedures. The subjects may withdraw consent at any time throughout the course of the trial. The informed consent process will be documented in the subject's research chart, as required by 21 CFR 312.62. The informed consent form will be signed (or fingerprinted) and personally dated by the subject and the person who conducted the informed consent discussion. The original signed informed consent form will be retained in the subject's chart and a signed and dated copy will be provided to the subject. The rights and welfare of the subjects will be protected by emphasizing to them that the quality of their medical care will not be adversely affected if they decline to participate in this study.

15.2.1 Mali Site Community Permission and Individual Informed Consent Process

15.2.1.1 Community Permission

Community permission will be obtained from village elders, family heads, and other community members after explanation and discussion of the study.⁴¹ The community permission process goes through the following steps:

- Study investigators/personnel explain the study to village leaders, including the village chief, family heads, women association, and elders.
- The village leaders then discuss the study with family heads and community members and relay any additional questions or concerns they may have to study personnel.

- The study and the informed consent process are explained in detail to heads of families by study investigators/personnel.

At the time of community permission, the need for both husband and wife to agree to avoid pregnancy for the specified period if a wife chooses to volunteer will also be addressed.

The individual informed consent process and form will be translated into French. The study team conducts careful word-for-word review of the study consent form, and will translate the consent orally into local languages, as the majority of potential study subjects do not read or speak French. Verification that the oral translations are accurate and that the potential subjects understand the contents of the informed consent form will be done by an independent witness who is not a member of the study team. An evaluation checklist is performed to make sure that the study is understood by the subjects before the enrolment.

15.2.1.2 Individual Informed Consent

Local households and families will be invited to come to the study clinic for review of the informed consent, and if the subject agrees to participate, the subject will sign or fingerprint (if illiterate) the consent form.

At the consenting visit, the subject will read the consent form or have it explained in cases of illiteracy. Individuals in each family will be separately consented and not all individuals from a household need to participate.

Subjects will be encouraged to ask questions, and then take a multiple-choice questionnaire (true/false) to evaluate consent comprehension. All incorrect responses will be reviewed with the subject, and he or she must verbalize understanding of all incorrect responses. A score of $\geq 80\%$ correct is required for enrollment. For subjects scoring less than 80%, study staff may choose to review study details again with subject and reassess comprehension with a repeat Malaria Comprehension Exam. At the discretion of the Investigator, any subject whose comprehension is questionable, regardless of score, may be excluded from enrollment.

The Malaria Comprehension Exam will be translated into French and administered orally in the native dialect in the case of potential subjects who cannot read. Study staff will use incorrect answers from the questionnaire to identify those areas of the informed consent that need further review with subject. This will help ensure that the subject has sufficient understanding before the consent form is signed. The subject may either sign the consent form immediately or later after further consideration. Subjects unable to read will place a fingerprint in the place of a signature. In addition, an independent witness will sign the consent form to attest that the consent was fully explained and all questions were answered.

